## **2. STUDY OBJECTIVES**

### **2.1. Primary Objective**

The primary objective of the study is to demonstrate the reduction of LDL-C with alirocumab 150 mg subcutaneous (SC) every 2 weeks (Q2W) in comparison to placebo after 12 weeks of treatment.

### **2.2. Secondary Objective(s)**

The secondary objectives of the study are:

- To evaluate the effect of alirocumab 150 mg Q2W on other lipid parameters (i.e., apolipoprotein [Apo] A-1 and B, non-high-density lipoprotein cholesterol [non-HDL-C], total cholesterol [TC], proportion of patients with 15%, 30%, and 50% LDL-C reductions, Lp(a), HDL-C, triglycerides [TG]) in patients with HoFH
- To evaluate the safety and tolerability of alirocumab 150 mg SC Q2W in patients with HoFH
- To assess the pharmacokinetics (PK) of alirocumab 150 mg SC Q2W in patients with HoFH
- To assess the potential development of anti-drug (alirocumab) antibodies

### **2.3. Other Objectives**

- Genotype information will be collected for all patients to characterize HoFH mutation status in order to explore potential differences in efficacy and safety
- To assess the effect of alirocumab on eligibility for apheresis (using German and US apheresis criteria)
- To assess the effect of alirocumab on quality of life using the EQ-5D QOL questionnaire

## **3. HYPOTHESIS AND RATIONALE**

### **3.1. Hypothesis**

Treatment with alirocumab for 12 weeks will result in a greater percent reduction in LDL-C from baseline than placebo treatment in patients with HoFH who are not already receiving PCSK9 targeted therapy.

## 3.2. Rationale

### 3.2.1. Rationale for Study Design

Patients with HoFH have persistently elevated LDL-C, which is a contributing factor to a number of health concerns, principally accelerated atherosclerosis resulting in premature CV disease. Despite treatment with LMTs such as pharmacological agents including statins, and mechanical removal of lipids by LDL apheresis, many patients with HoFH remain far from their LDL-C treatment goal. In a cohort study, the age of first CVD event was in the third decade of life in HoFH (Raal 2011). While this is later than the early teen years as seen before implementation of medical regimens such as statins, the need for more intensive treatments remain in order to delay the onset of CVD and occurrence of events.

This study is intended to demonstrate the efficacy and safety of alirocumab in patients with HoFH. The study population will include individuals  $\geq 18$  years of age. Diagnosis of HoFH will be based on either genotyping data or clinical criteria. The genetic definition will include all individuals considered to be true homozygotes, compound heterozygotes, or double heterozygotes for mutations in the LDLR, ApoB, PCSK9, or LDLRAP1 genes. In this study, however, individuals with history null/null LDLR mutations will be excluded because PCSK9 inhibitors, including alirocumab, will not be efficacious in those patients. This was confirmed in the evolocumab HoFH study (TESLA-B, TASSIG), where patients with null/null LDLR mutation status were treated with evolocumab, but did not have any response or had a minimal response to treatment.

Percent change in LDL-C from baseline will be the primary endpoint. Low-density lipoprotein cholesterol is an accepted surrogate endpoint for CV risk and has repeatedly been used as the primary endpoint for approval of multiple other HoFH treatments. This study is designed as a placebo controlled trial with the addition of alirocumab on top of patients' existing treatment regimens of maximally tolerated LMT, including lipid apheresis. This study will utilize an optional run-in period for those patients that have not yet achieved a stable background treatment regimen that will be required to be maintained throughout the double-blind treatment period. An add-on design is appropriate because removal of any therapies from the patient's existing treatment regimen will lead to an increase in LDL-C and possibly contribute to the serious CV sequelae seen in this disease. Treatment duration of 12 weeks for the primary endpoint will allow alirocumab to achieve steady state and exert its full effect on LDL-C. An additional 12-week open-label treatment period in which all patients will be administered alirocumab will allow further assessment of safety in this population.

### 3.2.2. Rationale for Dose Selection

Alirocumab 75 mg and 150 mg SC Q2W are the approved doses and is currently authorized in 40 countries worldwide (including the US, European Union, Canada, Norway, Iceland, Brazil, and Japan). The 150 mg SC Q2W dose has demonstrated saturation of free PCSK9 through the dosing interval and provides maximum efficacy. The need for a higher starting dose in hard-to-treat patients as characterized by a higher baseline LDL-C was seen in the Odyssey FH1, FH2 and HIGH FH studies. The Odyssey FH1 and FH2 studies enrolled patients with HeFH not controlled on maximally tolerated statins (with or without ezetimibe) and evaluated the addition of alirocumab 75 mg SC Q2W, with a possible up-titration to 150 mg SC Q2W, on LDL-C. Approximately 40% of the patients needed their dose titrated from 75 mg SC Q2W to 150 mg SC

Q2W, and the need for titration was a reflection of the baseline LDL-C value. Patients requiring up-titration had a mean LDL-C of 160 mg/dL (4.14 mmol/L) at baseline vs. 118 mg/dL (3.05 mmol/L) in those patients not requiring titration. The Odyssey HIGH FH study included patients with HeFH receiving maximally tolerated statin therapy and baseline LDL-C levels  $\geq$ 160 mg/dL (4.14 mmol/L) and used a starting dose of 150 mg SC Q2W. At this higher starting dose, alirocumab was able to reduce LDL-C by approximately 45.7% from baseline (Ginsberg 2016). Because patients with HoFH are proven to be a hard-to-treat population compared to non-FH and HeFH patients and will have a very high baseline LDL-C far from their target level, the dose of alirocumab proposed for this study is the highest approved dose, 150 mg SC Q2W.

In addition to being efficacious, alirocumab has a favorable safety profile. Overall, the most commonly occurring treatment-emergent adverse events (TEAEs), reported in a higher proportion of patients in the alirocumab group compared to placebo (ie, incidence  $\geq$ 2.0% in the alirocumab group) were: injection site reaction (7.2% vs 5.1%), nasopharyngitis (11.3% vs 11.1%), influenza (5.7% vs 4.6%), myalgia (4.3% vs 3.4%), urinary tract infection (4.8% vs 4.6%), diarrhea (4.7% vs 4.4%) and bronchitis (4.3% vs 3.8%) ([Praluent Product Insert](#)). No differences in the safety profile have been observed between the two approved doses of 75 mg and 150 mg.

It is expected that treatment with alirocumab 150 mg Q2W in patients with HoFH already receiving maximally tolerated LMT or LDL apheresis will be well-tolerated and have an acceptable safety profile while providing maximal LDL-C lowering effect.

### 3.2.3. Benefit / Risk Assessment

Patients with HoFH have extremely high LDL-C levels, are far from their target LDL-C, and will require significant reductions in LDL-C. Despite the approval of newer treatments including lomitapide and mipomersen, the need for more intensive therapies remain. PCSK9 inhibitors are a new addition to the armamentarium of LMT that has proven to profoundly decrease LDL-C. In TESLA-B, evolocumab on top of statins (with or without ezetimibe) in patients with HoFH showed a 23.1% mean reduction in LDL-C at week 12 ([Raal 2014](#)). In the Odyssey HIGH FH study, alirocumab reduced LDL-C by approximately 45.7% in patients with HeFH receiving maximally tolerated statin therapy and baseline LDL-C levels  $\geq$ 160 mg/dL (4.14 mmol/L) (Ginsberg 2016). Based on these data, it is expected that the addition of alirocumab to existing treatments will lead to significant LDL-C reductions in the HoFH population. The body of evidence from the statin literature shows that the relationship between LDL-C reduction and CV event reduction is approximately linear and for every 1 mmol/L (38.7 mg/dL) reduction in LDL-C there is a corresponding 22% risk reduction in CV events ([Cholesterol Treatment Trialists' Collaboration 2010](#)). Within the context of this study in the HoFH patient population, even a modest reduction in LDL-C may translate into significant benefit for these patients.

It is also expected that treatment with alirocumab will be well tolerated and have an acceptable safety profile. The accumulated safety information show that the most commonly occurring TEAEs with alirocumab were nasopharyngitis, injection site reactions, influenza, myalgia, musculoskeletal pain, and contusion. Moreover, the rates of these adverse events (AEs) were relatively low, ranging from 11.3% to 2.1% for the alirocumab treatment group (vs 11.1% - 1.6% in the placebo group) ([Praluent Product Insert](#)).

Taken together, these data show that the benefit/risk assessment of treatment with alirocumab in the HoFH populations is favorable.

## 4. STUDY VARIABLES

### 4.1. Demographic and Baseline Characteristics

Baseline characteristics will include standard demography (age, race, weight, height, etc), disease characteristics including lipid levels, mutation status, medical history, medication history and apheresis schedule (if applicable) for each patient.

### 4.2. Primary and Secondary Endpoints

#### 4.2.1. Primary Endpoint

The primary efficacy endpoint is the percent change in LDL-C from baseline to week 12 in the ITT population for alirocumab 150 mg Q2W as compared with placebo in patients with HoFH.

The percent change in LDL-C from baseline to week 12 is defined as:

$$\frac{100 \times (\text{LDL-C value at week 12} - \text{LDL-C value at baseline})}{\text{LDL-C value at baseline}}$$

For LDL-C analysis, both calculated and measured LDL-C values will be taken into account. In case both calculated and measured LDL-C values are available for the same sampling time point, the measured LDL-C will be considered. The baseline LDL-C value will be the last LDL-C value obtained before the first dose of double-blind-study drug. For randomized but not-treated patients, baseline will be defined as the last value before randomization. The LDL-C at week 12 will be the LDL-C value obtained within the week 12 analysis window, regardless of adherence to treatment (ITT estimand).

All calculated and measured LDL-C values (scheduled or unscheduled, fasting or not fasting) may be used for the primary efficacy endpoint, if appropriate, according to the above definition. The analysis window used to allocate a time point to a measurement will be defined in the statistical analysis plan (SAP).

#### 4.2.2. Secondary Efficacy Endpoints

##### 4.2.2.1. Key Secondary Efficacy Endpoints

- The percent change in Apo B from baseline to week 12 (ITT estimand).
- The percent change in non-HDL-C from baseline to week 12 (ITT estimand).
- The percent change in total cholesterol from baseline to week 12 (ITT estimand).
- Proportion of patients with  $\geq 15\%$  reduction in LDL-C at week 12 (ITT estimand).
- Proportion of patients with  $\geq 30\%$  reduction in LDL-C at week 12 (ITT estimand).
- The percent change in Lp(a) from baseline to week 12 (ITT estimand).

- Proportion of patients with  $\geq 50\%$  reduction in LDL-C at week 12 (ITT estimand).
- The percent change in HDL-C from baseline to week 12 (ITT estimand).
- The percent change in fasting TG from baseline to week 12 (ITT estimand).
- The percent change in Apo A-1 from baseline to week 12 (ITT estimand).

The same definition and rules apply to these key secondary efficacy endpoints as are applied to the primary efficacy endpoint.

#### 4.2.2.2. Other Secondary Efficacy Endpoints

- The percent change in LDL-C from baseline to week 12 in the modified (m)ITT population (Section 10.3.1), using all LDL-C values within the week 12 analysis window and during the efficacy treatment period (on-treatment estimand).
- The percent change in Apo B, non-HDL-C, TC, Lp(a), HDL-C, fasting TG and Apo A-1 from baseline to week 12 (on-treatment estimand).
- Proportion of patients with  $\geq 15\%$  reduction,  $\geq 30\%$  reduction, and  $\geq 50\%$  reduction in LDL-C at week 12 (on treatment estimand).
- The absolute change in the ratio of Apo B/Apo A-1 from baseline to week 12 (ITT estimand).

The efficacy treatment period is defined as the time from the first double-blind study drug injection up to 21 days after the last double-blind study drug injection, or the first open-label alirocumab injection (if applicable), whichever comes first.

#### 4.2.3. Safety Endpoints

- Safety parameters (AEs, laboratory data, vital signs, and electrocardiogram [ECG]) assessed throughout the study.

#### 4.2.4. Other Endpoints

- Exploratory relationships between HoFH genotype status and lipid parameters.
- The change in the proportion of patients who meet US apheresis eligibility criteria from baseline to week 12 (Goldberg 2011).
- The change in the proportion of patients who meet German apheresis eligibility criteria from baseline to week 12 (Schettler 2012).
- Response of each EQ-5D item, index score, and change of index score from baseline through week 12.

### 4.3. Pharmacokinetic Variables

The PK variable will be alirocumab serum concentration collected at specified sampling time.

#### 4.4. Anti-Drug Antibody Variables

Anti-drug (alirocumab) antibody status will be assessed.

- Total patients negative in the ADA assay at all time points.
- Pre-existing immunoreactivity - defined as either an anti-drug antibody (ADA) positive response in the assay at baseline with all post-dose ADA results negative, OR a positive response at baseline with all post-treatment ADA responses less than 4-fold baseline titer levels.
- Treatment emergent - defined as either any post-dose positive ADA response when baseline results are negative, OR any post-dose positive ADA response that is at least 4-fold over the baseline level when baseline is positive in the ADA assay.

Samples positive in the ADA assay will be assessed for titer.

- Titer category
  - Low (titer <1,000)
  - Moderate (1,000≤ titer ≤10,000)
  - High (titer >10,000)

Samples positive in the ADA assay will be assessed for neutralizing activity.

## 5. STUDY DESIGN

### 5.1. Study Description and Duration

This is a randomized, double-blind, placebo-controlled, parallel-group study to evaluate the efficacy and safety of alirocumab in patients with HoFH.

Approximately 74 patients will be randomized in a 2:1 ratio to receive either alirocumab 150 mg SC Q2W or matching placebo. Randomization will be stratified by apheresis treatment status (Yes/No).

The study will consist of up to 4 periods: an optional 4-week run-in period (for patients whose background medical LMT regimen or apheresis schedule and/or apheresis settings have not been stable prior to screening), a 2-week screening period, a 12-week double-blind treatment period, and a mandatory 12-week open-label treatment period ([Figure 1](#)). Patients not continuing on to another lipid lowering study will also undergo an 8-week follow-up period.

#### **Optional Run-in:**

***Apheresis therapy*** - Patients who are undergoing apheresis therapy must be on a stable weekly or every other week schedule. Patients whose schedule or apheresis settings that have not been stable for at least 8 weeks before the screening visit will enter a 4-week run-in period before the screening period. After the 4-week run-in period, patients whose lipid-apheresis schedule/settings remain stable (and have been stable for at least 8 weeks in total) will be eligible to enter the 2-week screening period. Additionally, all patients on LDL apheresis must be diagnosed based on genotype and, if genotype information has not been determined previously, they can enter the run-in to allow time, if needed, to determine their mutation status.

***Lipid-modifying therapy*** - Patients who are on background LMT that has not been stable for at least 4 weeks before the screening visit will enter a 4-week run-in period to stabilize their LMT before entering the screening period. Patients who have not been on a stable dose of mipomersen for 6 months prior to screening or on a maximum tolerated dose of lomitapide for 12 weeks prior to screening are excluded.

#### **Screening:**

Once on a stable background regimen as defined above, patients will enter a 2-week screening period. Initial eligibility will be determined during this screening period by standard screening procedures. A DNA sample will be collected for HoFH mutation status.

Patients should be on a stable low fat or heart-healthy diet throughout the duration of the study, starting at screening through the end of the double-blind treatment period and through the open-label treatment period.

Patients' exercise regimen should remain stable throughout the duration of the study, from screening, through the end of the double-blind treatment period and through the open-label treatment period.

The patient or caregiver will be trained to self-inject/inject using a dose of placebo during the screening period or at the first visit of the double-blind treatment period.

**Double-blind Treatment:**

Patients who meet all inclusion criteria and who meet none of the exclusion criteria will be randomized in a 2:1 ratio to receive:

alirocumab 150 mg SC Q2W

OR

matching placebo SC Q2W

Study drug administration during the double-blind treatment period will start on the day of randomization and will be administered immediately after completion of the LDL apheresis procedure (if applicable). For those patients not undergoing LDL apheresis, administration of study drug must be made after all samples for clinical laboratory evaluation have been obtained. The last injection during the double-blind treatment period will be on day 71/week 10.

For all patients undergoing LDL apheresis, all samples for clinical laboratory evaluation must be obtained immediately prior to the LDL apheresis procedure and prior to administration of study drug. Given the impact of LDL apheresis on lipid parameters, it is important to match the time of the baseline activities with the timing of the week 12 activities. This would mean that timing between the baseline sample collection relative to the most recently completed LDL apheresis procedure should match the timing of the week 12 sample collection relative to the most recently completed LDL apheresis procedure.

For all patients who are not undergoing apheresis, all samples for clinical laboratory evaluation must be obtained prior to administration of investigational medical product. The efficacy of alirocumab will be assessed by clinical laboratory evaluation of lipid levels at pre-specified time points throughout the study.

Patients who are receiving LMT or who are undergoing apheresis should maintain stable LMT and a stable apheresis schedule (as applicable) throughout the duration of the study, from screening through the end of the open-label treatment period/end-of-study visit (week 24).

Patients who prematurely discontinue study drug during the double-blind treatment period should be encouraged to remain in the study and undergo all double-blind study visits and procedures with the exception of dosing with study drug. At the time of study drug discontinuation, the patient should have, as soon as possible, an unscheduled visit with assessments normally planned at the end of the double-blind treatment visit (this should take place within 5 days of discontinuation of study drug, if possible).

[figure not shown]
**Open-label Treatment:**

To provide further safety data in this rare patient population, all patients will participate in an open-label treatment period. Regardless of treatment assignment in the double-blind treatment period, patients will receive open-label study drug (alirocumab 150 mg SC Q2W) starting at week 12 (day 85) and continuing through week 24 (end of open-label treatment period, last injection of study drug on day 155/week 22). Patients who are receiving LMT or who are undergoing LDL apheresis should continue a stable dose and regimen and a stable LDL apheresis schedule and settings (as applicable) throughout the duration of the open-label treatment period.

Upon completion of the open-label treatment period, the sponsor may offer each patient the opportunity to participate in an additional lipid-lowering clinical trial. The patient and investigator may decline participation in further treatment trials.

Patients who do not participate in another lipid-lowering study will undergo an 8-week follow-up period. A follow-up phone call will be made at week 32 (corresponding to the 70 day follow-up) to collect AE and concomitant medication information.

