### 8.1.2. Early Termination Visit

If for any reason the patient refuses to continue the study, the patient should undergo an unscheduled visit as soon as possible with assessments normally planned at the end of double-blind treatment visit if the patient is in the double-blind treatment period (week 12 visit assessments); if the patient is in the open-label treatment visit, then the end of the open-label treatment assessments should be used (week 24 visit assessments). This visit should take place within 5 days of treatment discontinuation, if possible. The patient should be followed for at least 70 days from the last dose of study drug or up to recovery or stabilization of any AE to be followed-up as specified in this protocol, whichever comes last.

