## 8.2. Study Procedures

### 8.2.1. Procedures Performed Only at the Screening/Baseline Visit

The following procedures will be performed for the sole purpose of determining study eligibility or characterizing the baseline population:

- medical/surgical history
- medication history
- demographics
- hepatitis B surface antigen
- serum pregnancy testing

On day 1, after completion of study assessments, collection of blood samples, LDL apheresis (if applicable), and the first dose of double-blind investigational study drug will be administered. The patient will be monitored at the clinical site for 30 minutes after the first dose. Subsequent doses of the investigational study drug must be administered subcutaneously Q2W. Doses of the investigational study drug should be administered at approximately the same time of day (based upon patient preference) throughout the study. After day 1, it is acceptable for dosing to fall within a window of  $\pm$  5 days, with the exception of the week 10 and week 22 doses, which will have a  $\pm$  3 day dosing window for patients not on apheresis and a +1 day dosing window for patients on apheresis since there are key efficacy assessments at week 12 and week 24.

In the event an injection is delayed by more than 7 days or completely missed, the patient should return to the original schedule of the investigational study drug dosing without administering additional injections. If the delay is less than or equal to 7 days from the missed date, the patient should administer the delayed injection and then resume the original dosing schedule. Site personnel will provide the patient/caregiver with detailed instructions for transport, storage, preparation, and administration of the investigational study drug.

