#### **9.4.6. Follow-up**

Adverse event information will be collected until the patient's last study visit.

Serious adverse event information will be collected until the event is considered recovered, chronic and/or stable, or fatal.

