##### Definitions

For safety variables, the following observation periods are defined:

- The pretreatment period is defined as the time from signing the ICF to before the first dose of double-blind investigational study drug.
- The double-blind TEAE observation period is defined as the time from first dose of double-blind investigational study drug to the last dose of double-blind investigational study drug + 70 days, or up to the day before first dose of open-label investigational study drug administration, whichever is earlier.
- The open-label TEAE observation period is defined as the time from first open-label study treatment administration to the last open-label study treatment administration + 70 days.
- The post-treatment observation period is defined as the time from the day after the end of the respective TEAE periods up to the patient's end of study.
- Pre-treatment AEs are defined as those that developed, worsened, or became serious during the pre-treatment period.
- Double-blind and open-label TEAEs are defined as those that developed, worsened, or became serious during the respective TEAE periods.
- Double-blind and open-label post-treatment AEs are defined as those that developed, worsened, or became serious during the post-treatment period.

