## 2.3. Study Plan

The study will consist of up to 5 periods: an optional 4-week run-in period (for patients whose background medical LMT regimen or apheresis schedule and/or apheresis settings have not been stable prior to screening), a 2-week screening period, a 12-week double-blind treatment period, a mandatory 12-week open-label treatment period, and an 8-week follow-up period ([Figure 1](#)).

Upon completion of the open-label treatment period, the sponsor may offer each patient the opportunity to participate in an additional lipid-lowering clinical trial. The patient and investigator may decline participation in further treatment trials.

Patients who do not participate in another lipid-lowering study will undergo an 8-week follow-up period. A follow-up phone call will be made at week 32 (Day 225) (corresponding to the 70-day follow-up) to collect AE and concomitant medication information.

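### The Week 32 safety call is fixed at Day 225 ±5 whatever the date of the last injection, so within permitted windows it can come as little as 62 days after that injection and leave the end of the 70-day open-label treatment-emergent period without active adverse event collection

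*Protocol*

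**What the plan says.** **Timing of the call.** Protocol Section 5.1 (Open-label Treatment) plans the "last injection of study drug on day 155/week 22" and then the Week 32 call: "A follow-up phone call will be made at week 32 (corresponding to the 70 day follow-up) to collect AE and concomitant medication information". SAP Section 2.3 repeats the equivalence: "A follow-up phone call will be made at week 32 (Day 225) (corresponding to the 70-day follow-up". Table 1 (Visit 9) gives the permitted range as Day 225 ±5. Footnote 10 limits the visit to patients who are not going on to another lipid-lowering study.

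**Length of the safety period.** Protocol Section 10.4.4.1 defines the open-label treatment-emergent period as the time from "first open-label study treatment administration to the last open-label study treatment administration + 70 days". SAP Section 4.7.1 uses the same end point and adds a residual treatment period covering days 22 to 70 after the last injection. SAP Section 4.3 applies the same +70 days to open-label concomitant medication.

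**When collection stops.** Protocol Section 9.4.6: "Adverse event information will be collected until the patient's last study visit". For patients with a Visit 9, that visit is the Week 32 call.

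**A minimum tied to the last dose.** Protocol Section 8.1.2 states: "The patient should be followed for at least 70 days from the last dose of study drug". That section concerns patients who refuse to continue the study.

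**Date of the last dose.** Protocol Section 8.2.1 gives a general dosing tolerance of ±5 days, "with the exception of the week 10 and week 22 doses, which will have a" tolerance of ±3 days off apheresis and +1 day on apheresis. The next paragraph of the same section adds: "If the delay is less than or equal to 7 days from the missed date, the patient should administer the delayed injection".

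**The concern.** The call is counted from Day 1, and the period it is meant to close is counted from the last injection. The two ends coincide only when dose and call both fall on their target days. Nothing obliges the site to wait until 70 days have passed for a patient who completes treatment, although a patient who withdraws must be followed for at least that long.

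The Amendment 2 rationale says the treatment-emergent period was lengthened from +21 to +70 days to gain safety information in a population in which the drug had not been studied, and that the call was added because of that change. A tolerance that lets the call come before day 70 works against its own purpose.

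At stake is the completeness of open-label safety data at the end of the window. If the time-to-event analysis that Protocol Section 10.4.4.1 allows for selected events is run, event-free patients are censored at the end of the treatment-emergent period and not at last contact. A patient called early would then be credited with a few event-free days that nobody observed.

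**Working it through.** **Inputs**
- Planned last open-label injection: Day 155 (Protocol 5.1).
- Permitted call days: 225 − 5 = 220 to 225 + 5 = 230, which is 11 days (Table 1).
- Week 22 dosing window: Day 152 to 158 off apheresis, Day 155 to 156 on apheresis (Protocol 8.2.1).
- Late-dose rule, if it reaches the Week 22 dose: 155 + 7 = Day 162 (Protocol 8.2.1).
- End of the open-label treatment-emergent period: last dose + 70 (Protocol 10.4.4.1, SAP 4.7.1).

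**The plan's own figure.** Week 22 is 22 × 7 + 1 = Day 155 and Week 32 is 32 × 7 + 1 = Day 225. The interval is 225 − 155 = 70 days, so the stated equivalence is exact at the target days.

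**Formulas**
- Interval = call day − last-dose day.
- Uncovered days = max(0, last-dose day + 70 − call day).

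| Last dose | Basis | Period ends | Interval, call on Day 220 / 225 / 230 | Uncovered days, same calls | Permitted call days before day 70 |
|---|---|---|---|---|---|
| Day 152 | 3 days early, off apheresis | Day 222 | 68 / 73 / 78 | 2 / 0 / 0 | 2 of 11 |
| Day 155 | on schedule | Day 225 | 65 / 70 / 75 | 5 / 0 / 0 | 5 of 11 |
| Day 156 | 1 day late, on apheresis | Day 226 | 64 / 69 / 74 | 6 / 1 / 0 | 6 of 11 |
| Day 158 | 3 days late, off apheresis | Day 228 | 62 / 67 / 72 | 8 / 3 / 0 | 8 of 11 |
| Day 162 | 7 days late, only if the late-dose rule applies | Day 232 | 58 / 63 / 68 | 12 / 7 / 2 | 11 of 11 |

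The last column counts calendar days. It is not a forecast of how often short intervals will occur, because the documents give no distribution of dose or call dates.

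**Share of the window.** 5/70 = 7% for an on-time dose, 8/70 = 11% for a dose three days late, and 12/70 = 17% on the late-dose reading.

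**Who cannot be affected.** A call on Day 220 covers 70 days for any last dose on or before Day 220 − 70 = Day 150. Patients who stopped drug well before Week 22 and stayed on schedule are therefore fully covered.

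**Serious events.** Protocol 9.4.2 keeps serious events with onset within 30 days of end of study reportable if the investigator is informed. After the earliest call this runs to 220 + 30 = Day 250, beyond the latest possible period end of Day 232.

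**The case against.** The strongest case for the plan is that it is right at its targets. A ±5-day tolerance on a phone call is ordinary, and many permitted combinations give 70 days or more; the full range is 58 to 78. That stands, and it limits the size of the point. It does not remove the point, because this call has one stated purpose and half of its tolerance lies on the wrong side of it for an on-time dose.

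A reader might make four stronger inferences that the documents do not support.
- **That compliant patients can be called at 58 days, or that no permitted call reaches day 70.** This requires the 7-day rule to override the narrower Week 22 window. Section 8.2.1 contains both and does not say how they combine. Within the Week 22 window the minimum is 62 days, or 64 on apheresis.
- **That all adverse events in the uncovered days are lost.** Serious events stay reportable for 30 days if the investigator learns of them, and fatal or drug-related ones beyond that. What lapses is active collection, so the likely loss is mainly non-serious events and concomitant medication.
- **That the safety tables present every patient as followed for 70 days.** The definitions assign events to periods and do not assert complete follow-up. SAP Section 7 plans, at the first-step analysis, a summary of patients with insufficient follow-up, though it does not define the term.
- **That the comparison of alirocumab with placebo is affected.** For patients entering the open-label period, the double-blind treatment-emergent period closes before the first open-label dose. Open-label safety is descriptive.

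It could also be argued that collection continues after the call, because Section 9.4.1 records events up to the end of study and Section 5.1.1 defines that as the last patient's last visit. That wording should be aligned with Section 9.4.6, but no contact after the call is scheduled through which such events would be collected.

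**Conclusion.** The point holds as a modest gap in safety follow-up that is worth correcting. With no deviation from the schedule, the call can come 65 days after an on-time last dose, 64 days after a dose one day late on apheresis, or 62 days after a dose three days late off apheresis. That leaves 5 to 8 days of the 70 without active collection when the call is made at its earliest. The 58-day interval and 12 uncovered days are conditional on the unresolved late-dose reading.

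The effect is confined to open-label descriptive safety in patients who have a Visit 9. How many patients are exposed cannot be stated, since the documents give neither the number entering a further lipid-lowering study nor the spread of dose and call dates. The conclusion assumes that Visit 9 is the last routine contact, as Table 1 shows.

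**What to change.** In Protocol Table 1 and Section 5.1, and in SAP Section 2.3, schedule Visit 9 no earlier than the later of Day 225 and the actual last open-label injection + 70 days, with a one-sided window, for example +0/+10 days.

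**Check.** The earliest call becomes Day 225 for a last dose on Day 152 or 155, Day 226 for Day 156, Day 228 for Day 158 and Day 232 for Day 162. Uncovered days are 0 in every case, whichever way the late-dose question is settled.

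**Why a later-of rule.** Protocol Section 7.4.2 keeps patients who stop drug but remain in the study on the original schedule through the follow-up call. Counting from the last injection alone would pull their call forward. A last injection on Day 71, for example, would give Day 141, before the Week 24 visit on Day 169. The Day 225 floor keeps their planned call date.

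**Cost.** Some calls move a few days later, and the latest permitted call for an on-time dose moves from Day 230 to Day 235. No visit or sample is added.

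Separately, the Week 22 dosing window and the 7-day delayed-dose rule in Protocol Section 8.2.1 must be reconciled. No view is taken here on which should govern.
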